#### 6.2.2 **Visit 2: Harvest Biopsy (EVPOME group only)**

At this time, a 6 mm in diameter supra-periosteal circular biopsy will be harvested for fabrication of the EVPOME from Group 1 subjects. Co-Investigators will perform the biopsy procedure. This biopsy will be performed at the school of dentistry research clinic. Intraoral photographs will also be taken at this time. A stent will be placed at this time if needed.

*Biopsy procedures:* All subjects will be prepped and draped in a sterile fashion prior to intraoral biopsies. Anesthesia will be obtained by local infiltrations and/or blocks. Tissue will be harvested using a 6mm punch. If bleeding is not controlled under gauze tamponade, a hemostatic collagen sponge will be placed and a cyanoacrylic dressing will be topically applied over the wound. Subjects will be given routine post-operative instructions to include a prescription for analgesia.

*Specimen handling:* The 6 mm biopsy specimen will be placed in a specifically prepared transport medium, containing 500.0ml DPBS (Dulbecco's Phosphate Buffered Saline) w/o  $\text{Ca}^{2+}$  &  $\text{Mg}^{2+}$  containing 0.54 g D-Glucose, 62.5 mg Gentamicin and 500.0  $\mu\text{g}$  Fungizone. The biopsy is immediately delivered to the CTML for oral keratinocyte dispersion and culture. The specimen will be labeled with pre-printed labels from the CTML with protocol number and subject study number.

A visual analog scale of pain will be taken at this time for group I and subjects will also be questioned about any adverse events.

#### 6.2.3 **Visit 3: Baseline: Intraoral Grafting of EVPOME or POM Grafts**

Grafts will be applied as determined by the randomization schedule. Group 1 subjects will undergo intraoral grafting of EVPOME and Group 2 subjects will receive POM that will be harvested at this time from the donor site, palate. For Group 1 subjects, before release of the EVPOME for grafting from the CTML, glucose utilization will be measured and determined as percent of glucose utilized by the EVPOME during the final days of laboratory incubation. Gram stain analysis will be performed on culture media that the EVPOME was grown in during the final day of incubation. Preliminary results of in-process sampling to determine the sterility (aerobic, anaerobic, and fungal cultures) of the product will

3/28/2017

be reviewed. Results of in-process mycoplasma testing will be reviewed. Analysis of in-process sampling for endotoxin will also be reviewed. If the device fabrication is unsuccessful, the subject will be given the opportunity to have a second palatal or retromandibular trigone (location is at the discretion of the principal investigator and the surgeon) biopsy taken for production of another EVPOME device.

Every effort will be made to maintain contact with the subject for safety data should the subject decline a second biopsy and withdraw from the study to pursue standard of care treatment. It is important to note that in our completed Phase I clinical trial we did not have to abort any procedure because of in-processing difficulties in not achieving our release criteria of passing the sterility tests and satisfying glucose consumption over the last 24 hours. Samples of spent media that the EVPOME was grown in may be stored and analyzed for proteins or other cell secretions in order to better understand graft success or failure.

EVPOME and POM grafts will be sutured and assessed to assure they are immobile. Subjects will be given standard post-operative instructions which may include analgesics and antibiotics per standard of care.

Intraoral photographs will also be taken at this time. A maxillary stent will be placed at this time for the POM subjects.

A visual analog scale of pain will be taken at this time for both group I and II and subjects will also be questioned about any adverse events.

#### 6.2.4 **Visit 4: Post-operative (Post-grafting)**

Routine post-operative visits at Week 1 +/- 3 days post-grafting will include an oral examination. Intraoral photographs will also be taken at this time. A visual analog scale of pain will be taken, and subjects will also be questioned about any adverse events.

#### 6.2.5 **Visit 5: Post-operative (Post-grafting)**

Routine post-operative visits at Week 2 +/- 3 days post-grafting will include an oral examination and clinical assessments, including degree of epithelialization and percent contracture.

Measurement of the maximum distance between the peripheral borders of the graft in both the x and y axis will be taken to assess percent of graft contracture. Laser Doppler flowmetry measurements will be taken with the pre-fabricated template at the approximate geometric center of the graft and on the contralateral side of the jaw as the graft placement. This will be done after stent removal. per this protocol:

LDF measurements will be with the subject resting in supine position, and at a

room temperature. A flexible probe (PR407, Perimed) will be used to obtain the measurements. The flowmeter will be calibrated before taking any measurements. Gingival blood-flow data will be reported in perfusion units (PU) and collected on the wideband setting. Voltage output values will be stored on an encrypted PC computer for storage and subsequent analysis.

Intraoral photographs will be taken. A visual analog scale of pain will be taken, and subjects will also be questioned about any adverse events.

#### 6.2.6 **Visit 6: Clinical Assessment and Biopsy of Grafts**

Visit 6 will occur 4 weeks after the graft procedure +/- 3 days. Grafted sites of all subjects will be evaluated through clinical observation and photographs. Measurement of the maximum distance between peripheral margins of the grafts will be taken to assess degree of contracture as performed previously in Visit 5. Three variables of keratinization, contracture and micro-vascularization will be evaluated to assess outcomes

A 2 mm biopsy of the central portion of the surface of the graft will be obtained for evaluation, under local anesthesia, after the LDF measurements have been completed. Histology and immunohistochemistry evaluations will be performed on the biopsied tissue. Intraoral photographs will be taken. We expect that the EVPOME will have a higher number of microvessel ingrowth at the early stages after grafting compared to the POM. We also expect that epithelium will be present and will mature at an earlier stage after grafting compared to the POM.

***Rationale for selection of 4 weeks for timing of biopsy:*** The first 2 weeks after grafting, a pressure dressing (surgical stent) is in place. At 3 weeks, the overlying mucosa is immature and friable. Based on previous experience, four weeks is the earliest time period we can detect a mature graft. If a graft fails, it will do so within the first 4 weeks. This supports the rationale for selection of this time period. Previous clinical studies took the biopsy at 6 months. We believe this time period is too far beyond the surgery date and would diminish the differences seen between the two types of grafts. The EVPOME graft is approximately 0.75-1.0 mm thick. It has been previously shown that it takes 10-11 weeks for a free mucosal graft of this thickness to reach maturity. Others showed that in 4 weeks, free grafts are keratinized.

Intraoral photographs will also be taken at this time. A visual analog scale of pain will be taken, and subjects will also be questioned about any adverse events.

#### 6.2.7 **Visit 7: Clinical Assessment**

A clinical assessment and oral examination visit to measure subject comfort and

3/28/2017

progress will be scheduled at Week 8 +/- 1 week. This visit will also include measurements for degree of graft contracture, as well as other periodontal measures for adjacent teeth and implant (if present). Intraoral photographs will be taken. A visual analog scale of pain will be taken, and subjects will also be questioned about any adverse events.

#### **6.2.8 Visit 8: Clinical Assessment and End of Study**

A clinical assessment and oral examination visit will be performed to measure subject progress at Week 24 +/- 1 week (6 months). This visit will also include measurements for degree of graft contracture, as well as periodontal measures for adjacent teeth and implants (if present). Intraoral photographs may be taken at the investigator's discretion. A visual analog scale of pain will be taken, and subjects will also be questioned about any adverse events. At this time point, the subject's participation in this study will be completed.

#### **6.2.9 Long-term Follow-up**

At 9 and 12 months, the subject will be phoned to discuss any Adverse Events or concerns with the graft site. At approximately 12 months, the subject will return for a standard of care visit and clinical examination with their primary oral surgeon/restorative dentist for further dental rehabilitation. Any issues with the study graft will be recorded in the patient dental records.

#### **6.2.10 Early Withdrawal/Study Discontinuation Evaluations**

Upon discontinuation, subjects will be evaluated following the Visit 8/ End of Study procedures listed in the Schedule of Evaluations (Table 1, Section 6.1).

#### **6.2.11 Off-Study Requirements**

Subjects who discontinue early from the study for any reason after Visit 3 will be asked to return to perform study procedures as described in Visit 8/End of Study. All subjects who discontinue or complete the study will also be asked to report any Serious Adverse Events that occur within 30 days of completion/withdrawal from the study.

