### Interventions and Duration

The outcomes data in patients treated with experimental EVPOME soft tissue intraoral grafting procedure will be compared to the outcomes in patients treated with POM, which is the standard of care procedure. Those randomized to the experimental group will undergo a small 6mm palatal punch biopsy. Keratinocytes extracted from the punch biopsy will be harvested and expanded *in vitro* then seeded onto the AlloPatch®. This process will take approximately 30 days depending on the period of time needed for cell amplification. EVPOME or POM will then be grafted onto the oral defect and secured with absorbable sutures. At Week 4, after grafting, a 2 mm punch biopsy will be taken to assess degree and maturity of keratinization and microvessel ingrowth.

Throughout the duration of the study, the subject will return for subsequent study visits to assess oral health and graft healing, contracture, and revascularization. The subjects will attend 7-8 scheduled study visits, one of which will be the grafting procedure, over a period of approximately 30 weeks. The post-operative follow-up period will include 5 study visits over approximately 24 weeks.

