## 5.2 Handling of Study Interventions

All of the AlloPatch® used in this study will be procured and stored by UM Clinical Tissue Manufacturing Laboratory (CTML) for use on this study. When subjects are randomized to EVPOME arm, AlloPatch® will be available to the study team in the Clinical Tissue Manufacturing Laboratory where EVPOME manufacturing will take place.

For subjects randomized to the EVPOME arm of the study, during Visit 2, surgeon co-investigators will extract a single 6 mm circular palatal punch biopsy for EVPOME manufacturing. In the case in which the subject wears an upper prosthesis the harvest biopsy will be taken from the retromandibular trigone region in the mandible. A member of the EVPOME manufacturing team will provide pre-labeled transportation vessels, a primary vessel containing transportation media in which the biopsy will be placed, and a secondary containment vessel into which the primary transportation vessel will be placed.

The surgeon and the EVPOME manufacturing technician will document the chain of custody by completing the transportation of punch biopsy record. The manufacturing technician will transport the biopsy and record to the Clinical Tissue Manufacturing Laboratory and begin EVPOME manufacturing. EVPOME manufacturing procedures provide detailed instructions for the manufacture, control, and release of the EVPOME product.

On the day that the EVPOME engraftment is to occur, the Principal Investigator, [name], or the Clinical Tissue Manufacturing Laboratory Manager will review the EVPOME manufacturing records and determine if the EVPOME meets required specifications (passing the sterility tests and satisfying the release criterion of glucose consumption over the last 24 hours) for engraftment. If the EVPOME is released by the Principal Investigator or the CTML Manager, the certificate of analysis is signed. The manufacturing staff will then transport the EVPOME to the surgeon in the surgical suite and attain site staff signature of receipt. If the EVPOME is determined to be unsuitable for engraftment, then there are two paths of accountability for the unused EVPOME. One of the following two paths will be used and documented on the EVPOME certificate of analysis:

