Women of childbearing potential must agree to use a medically acceptable means of birth control and test negative on the Screening Visit urine pregnancy test. Intraoral photographs will also be taken.

Lastly, upper and lower jaw impressions will be taken for stent fabrication to protect the donor site and for use in LDF measurements

Subjects randomized to Group 1 (EVPOME), will be scheduled for Visit 2 to undergo a palatal punch biopsy/tissue harvesting which will be the source of autogenous cells used to make the cellular component of the EVPOME, within 14 days of determination. Subjects randomized to Group 2 (POM) will bypass Visit 2 and proceed to scheduling of harvesting of palatal donor tissue graft and intra-oral grafting at recipient site (Visit 3) upon completion of screening procedures.

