### 9.3 Sample Size and Accrual

We propose to have 60 subjects to give clinical and histological endpoints of interest at the primary assessment time of 4 weeks post graft. We expect no more than 6 subjects to potentially drop out of the study before providing Week 4 data, and thus will enroll 66 patients in total. With an estimated enrollment of 1 out of 5 screened patients, we expect to have a pool of over 330 patients over two years from which to select 66 subjects (33 subjects per group over two years) that will be randomized equally to one of the two groups - EVPOME and POM grafts. The randomization list will be prepared electronically in advance by the biostatistician and transferred to the MICHR statistics group for incorporation into the TATUM system. Randomization will be stratified by smoking status.

The primary clinical endpoint is the degrees of keratinized tissue. Secondary outcomes are contracture and wound healing index. Ancillary endpoints include the presence or absence of a continuous epithelial layer, the degree of vascular ingrowth, the LDF measurement of gingival blood flow. The main aim is to show that EVPOME treatment give comparable clinical and histological results when compared with POM treatment. It is also expected that the EVPOME will cause less patient discomfort and pain, and have a better color rendition to the surrounding tissue than the POM. Hence, we expect EVPOME to show better outcomes for pain, color rendition, and microvessel infiltration than POM, while showing comparable outcomes on primary endpoints of keratinized tissue and graft contracture or histological endpoints compared with POM. Sample size is calculated to show near equivalence of the two groups for primary and secondary outcomes. Sample size calculation and power consideration are provided following the data analytic plan described for each outcome.

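### Subjects randomized to EVPOME but never grafted have no Week 4 outcome and no stated place in the analysis, so the equivalence comparison would in practice hold only released EVPOMEs

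*Combined protocol and SAP*

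**What the plan says.** Sections 4.3 and 6.1 place randomization at Visit 1. The arms then follow different paths. Section 6.2.1: "Subjects randomized to Group 2 (POM) will bypass Visit 2 and proceed to scheduling of harvesting of palatal donor tissue graft". The EVPOME arm has a harvest biopsy and then manufacture, of which the synopsis says: "This process will take approximately 30 days depending on the period of time needed for cell amplification". Section 5.2 puts the release decision on the day of grafting and provides for rejection: "If the EVPOME is determined to be unsuitable for engraftment, then there are two paths of accountability for the unused EVPOME".

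Section 6.2.3 covers failed manufacture. It says "If the device fabrication is unsuccessful, the subject will be given the opportunity to have a second palatal or retromandibular trigone" biopsy, and then: "Every effort will be made to maintain contact with the subject for safety data should the subject decline a second biopsy and withdraw" to have standard care.

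Three sections cover assessment after discontinuation:
- Section 6.2.11: "Subjects who discontinue early from the study for any reason after Visit 3 will be asked to return to perform study procedures" of the end-of-study visit. It also asks everyone who leaves to report serious adverse events for 30 days.
- Section 6.2.10 sends discontinuing subjects to the Visit 8 procedures, with no condition that they were grafted.
- Section 8 does the same for the discontinuations it lists.

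Section 9.5 bases the primary comparison on Week 4 after grafting. Section 9.3 sizes the trial on subjects who reach that point: "We expect no more than 6 subjects to potentially drop out of the study before providing Week 4 data". That allowance is not split by arm or cause. Section 9 has no definition of an analysis population, no missing-data rule, and no rule for subjects randomized but never grafted.

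**The concern.** Manufacturing loss after randomization can occur in one arm only. A subject lost that way has no graft date, so no Week 4 visit and no primary outcome, and nothing in Section 9 brings the subject back into the comparison. The analysed EVPOME group would then be the randomized group minus those whose product failed and who left, set against a palatal (POM) group with no corresponding filter.

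For an equivalence or non-inferiority aim, removing failures from the experimental arm pushes toward the conclusion the trial hopes to reach. It also changes the question. The trial would show whether a released EVPOME matches POM, not whether assigning a patient to EVPOME does as well as assigning POM.

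**Working it through.** **Inputs from the documents.** KM (keratinized mucosa) width under POM: mean 3.70 mm, SD 0.65 mm; margin ±0.55 mm; two-sided 95% interval; 30 evaluable per arm (all Section 9.5). Enrolment 66, or 33 per arm, with up to 6 losses before Week 4 (Section 9.3). Eligibility ceiling for baseline KM width: 3 mm (Section 4.1).

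**Inputs by assumption.** The number of EVPOME failures, k, out of 33, because no rate is given. No other losses. Released EVPOME equal to POM. An ungrafted subject falls short of 3.70 mm by d = 0.7 mm (width 3.0, the eligibility ceiling) or d = 1.7 mm (width 2.0, assumed).

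**Step 1: reproduce the plan's figure.**
- SE = 0.65 × √(1/30 + 1/30) = 0.168; margin of error = 1.96 × 0.168 = 0.33.
- Equivalence power = 2Φ(0.55/0.168 − 1.96) − 1 = 2Φ(1.317) − 1 = 81.2%, matching the stated 80% or more.
- The one-sided version gives Φ(1.317) = 90.6%, consistent with the remark that non-inferiority power is larger.

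**Step 2: is lost sample size the problem?** Put all 6 allowed losses in the EVPOME arm, giving 27 against 33. SE = 0.65 × √(1/27 + 1/33) = 0.169, and power is 80.7%. So numbers are not the issue; what is estimated is.

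**Step 3: effect of counting the failures.** With f = k/33:
- Shift in the all-randomized difference = −f × d.
- EVPOME-arm SD = √(0.65² + f(1 − f)d²).
- Probability of concluding equivalence = Φ((0.55 − fd)/SE − 1.96) + Φ((0.55 + fd)/SE − 1.96) − 1.

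Example, k = 3 and d = 1.7: shift = −(3/33) × 1.7 = −0.15 mm; EVPOME SD = √(0.4225 + 0.0826 × 2.89) = 0.813; SE = √((0.813² + 0.65²)/33) = 0.181; probability 56%.

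| EVPOME failures | Failures dropped | All randomized, d = 0.7 | All randomized, d = 1.7 |
|---|---|---|---|
| 1 (3%) | 0 mm, 85% | −0.02 mm, 85% | −0.05 mm, 79% |
| 3 (9%) | 0 mm, 84% | −0.06 mm, 81% | −0.15 mm, 56% |
| 6 (18%) | 0 mm, 81% | −0.13 mm, 70% | −0.31 mm, 22% |

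Each cell gives the expected difference and the probability of concluding equivalence. The largest shift takes 0.31/0.55 = 56% of the margin and leaves 0.24 mm for any true shortfall of released grafts. A released-only comparison would show none of this.

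**Step 4: the opposite case.** Section 6.2.3 describes withdrawal to have standard care. If such a subject is treated and then measured, the shift could be near 0, and the all-randomized analysis could itself lean toward equivalence. Neither set suffices alone.

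**The case against.** Several stronger readings are tempting, and the documents do not support them.

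- A reader might infer that subjects lost before grafting are followed for safety only. Section 6.2.10 sends discontinuing subjects to the Visit 8 procedures without a grafting condition, and the Section 6.1 footnote lists keratinization among the clinic assessments. What is documented is a conflict with 6.2.11. Even so, an evaluation at a pre-graft withdrawal gives no Week 4 outcome.
- A reader might infer that the plan prescribes a completer analysis. It does not; exclusion follows from silence combined with a graft-anchored endpoint. That silence leaves the choice of set until after the data are seen.
- A reader might infer that grafts lost after placement also leave the primary comparison. Section 9.2.1 measures KM width from the ridge crest, or the implant or tooth margin, to the mucogingival line, which needs no graft borders. Graft loss can occur in either arm, and Section 6.2.6 says "If a graft fails, it will do so within the first 4 weeks", so the Week 4 visit should capture it.

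Three mitigating points stand in part. The second-biopsy offer keeps in the trial those who accept it. Phase I had no procedure aborted for manufacturing difficulties, but Section 2.2 says it used AlloDerm, which the protocol considers very similar to the AlloPatch used here; its number of subjects is not given, and that record does not cover withdrawal while waiting. POM subjects can also wait and withdraw, since the screening window runs to 90 days in both arms; only manufacturing loss is specific to EVPOME.

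Finally, Section 9.1 frames the hypothesis around a grafting material, so an as-grafted comparison is a legitimate Phase II question. That supports reporting it, not leaving the set undefined.

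**Conclusion.** The concern holds in this form: randomization precedes a manufacturing and release step confined to the EVPOME arm; Sections 6.2.3, 6.2.10 and 6.2.11 disagree on assessment of those lost before grafting and give no Week 4 value for them; and Section 9 does not say how they are counted. In practice the equivalence comparison would rest on EVPOME subjects whose product was released.

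The size is conditional. Under the stated assumptions the shift alone stays inside the 0.55 mm margin for up to 6 failures, but it can use more than half of it. With no failures the problem disappears; with standard care before measurement it may be negligible. The direction of a released-only analysis is nonetheless predictable, so the point should be settled before data are seen.

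**What to change.** - **Sections 6.2.10 and 6.2.11:** reconcile them by removing from 6.2.11 the limit to discontinuations after Visit 3.
- **Section 6.2.3:** ask every randomized subject, grafted or not, for one KM-width measurement at a time fixed from randomization or the planned graft date, and record any non-study graft received by then. A fixed anchor is needed because Day 0 is defined by grafting.
- **Section 9.5, analysis sets:** analyse all randomized subjects in their assigned arm, report the as-grafted set alongside, and require both to support equivalence.
- **Section 9.5, sensitivity analysis:** give never-grafted subjects their screening KM width (gain 0). Section 6.1 schedules clinic assessments at screening but words their content as optional, so KM width at that visit should be made mandatory.
- **Reporting:** give release failures and pre-graft withdrawals by arm.

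The cost is one non-invasive measurement in a few subjects, one added analysis, and a result that may look less favourable to EVPOME.
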